2. STUDY SUMMARY

Survival rates in cancer continue to improve, with over 2 million adult cancer survivors in the UK, projected to increase to 4 million by 2030. Around 25% of these survivors require treatment for clinical levels of emotional distress. Current pharmacological treatments are not very effective and are not well tolerated by patients, who prefer psychological treatments. However, meta-analyses of well-controlled studies of psychological treatments indicate that these achieve only small effect sizes. Reflecting this limited efficacy in the face of the need for psychological treatment, the National Cancer Survivorship Research Initiative highlighted development and evaluation of practically feasible interventions for depression and anxiety in cancer survivors as an urgent research priority. It is recognised that current influential psychotherapeutic approaches need to be modified to meet the specific needs associated with cancer. However modifications have been pragmatic rather than theory-driven and have not improved efficacy.

Our study addresses the stages of ‘development’ and ‘piloting and feasibility’ in MRC guidance on intervention development, albeit with a relatively well-defined starting point given existing evidence for efficacy of MCT in other settings and promising preliminary evidence of applicability in cancer. We will conduct a phase I open trial to test the potential efficacy of group MCT in cancer survivors and the hypothesised causal metacognitive mechanisms underpinning treatment response. The evidence from this open trial will therefore allow us to progress to the next step in translating group MCT for cancer survivors: a randomised phase II controlled trial against the current gold standard approach, namely cognitive behaviour therapy.

KEYWORDS: Group Metacognitive Therapy; Cancer Survivors; Open Trial; Anxiety; Depression

Title:	An Open Trial of Group Metacognitive Therapy for Anxiety and Depression in Cancer Survivors (GMAC Study)
Design:	An open trial (single arm, single site) with follow-up at 3 and 6 months.
Aim:	To conduct an open trial of group MCT for cancer survivors experiencing clinically significant emotional distress.
Objectives:	
 1. To obtain evidence of potential efficacy of group MCT in alleviating emotional distress in cancer survivors. 2. To assess the acceptability of the intervention to patients. 3. To obtain data to inform sample size calculations for a subsequent Phase II trial 4. Determine whether group MCT for cancer survivors can be easily delivered in routine clinical practice
Measures:	
Primary endpoint: Severity of depression and/or anxiety symptoms at post-treatment, and at 3 and 6 months follow-up, measured by the full scale score on the Hospital Anxiety and Depression Scale (HADS; [33]).
 
Secondary endpoints: Cognitive Attentional Syndrome-1 [19]; Fear of Cancer Recurrence Inventory [35]; Impact of Events Scale-Revised (IES-R) [36]; Metacognitions Questionnaire-30 (MCQ-30) [37]; Functional Assessment of Cancer Therapy-General (FACT-G) [38].

Population:	Patients who are referred to the Clinical Health Psychology Service experiencing clinically significant distress, operationally defined as a score of ≥ 15 on the full scale score on the HADS [32].
Intervention:	The intervention will constitute 6 sessions of group MCT. Clinical psychologists trained in group MCT will deliver the therapy to groups of 4-8 patients referred to the Liverpool psycho-oncology service, who meet study criteria and consent to participate.
Study duration:	15 months maximum

3. BACKGROUND

There are over 2 million adult survivors of cancer in the UK, projected to increase to 4 million by 2030 [1]. Survivors are at increased risk of clinically significant distress. A population-based survey [2] reported 6% prevalence of psychiatric disorders in survivors; double that in the non-cancer comparison group, even when socio-demographic and clinical correlates were controlled. Furthermore, although not meeting specific diagnostic criteria, 25% of patients report clinically significant anxiety and depression [3]. Therefore, around 500,000 people have cancer-related distress warranting intervention. Our proposal addresses the need for effective help for this large population. We will study patients from tumour groups that provide the main populations of survivors including, but not limited to breast (BCa), prostate (PCa) and colorectal (CRCa). In each, distress is more prevalent than in the normal population. In PCa, incidence of anxiety and depression 3 years post-diagnosis is 23% and 26%, respectively [4]. In BCa, incidence of depression, anxiety or both, defined by meeting full or borderline diagnostic criteria, is 25% 4 years post-diagnosis [5]. Although neglected in other cancers, post-traumatic stress disorder (PTSD) affects 5% of BCa patients [6], with

troubling symptoms of PTSD affecting 34% of patients 5 years post-diagnosis [7]. Emotional distress has been less explored in CRCa, but evidence indicates clinical depression or anxiety in 22% 5 years post-surgery [7]. Emotional distress reduces quality of life and, in the context of cancer survivorship, causes wider damage, increasing pain and fatigue[8, 9], reducing treatment adherence and impairing treatment decision-making[10], and increasing demand for, and cost of, physical health care[11, 12]. Given the wide-reaching implications of emotional distress in cancer survivors, and patients' preference for psychological over pharmacological treatments, highly efficacious treatments are needed.

4. RATIONALE FOR CURRENT STUDY

Meta-analyses of well-controlled studies indicate that current “gold standard” psychological and pharmacological treatments achieve only modest effect sizes [14-17]. Cancer survivors therefore need researchers to develop and evaluate psychological treatments that potentially have a better 'fit' with the cancer context, and are linked to theoretical models applicable to diverse forms of distress. Specifically, an intervention which identifies and modifies core psychological processes underpinning multiple forms of distress would offer the most promise to cancer survivors.

Our solution lies in recent developments of the area of ‘metacognitive’ theory and metacognitive therapy in mental health. Metacognitive therapy is derived from a trans-diagnostic model of metacognitive processes in psychopathology, the Self-Regulatory Executive Function (S-REF) model [18]. According to this model, emotional disorders are maintained by the cognitive-attentional syndrome (CAS) which comprises three processes: (i) perseverative thinking (worry and rumination); (ii) attentional strategies (monitoring for signs of potential threat); and (iii) counterproductive coping strategies (e.g. thought suppression and avoidance). Applying this to cancer survivors, multiple factors can temporarily activate the CAS, such as fears of recurrence or rumination about implications of cancer on work and family roles. For most patients, resulting worry and rumination are transient but, in those who will become depressed or anxious, sustained rumination (e.g. about current impact on family) or worry (e.g. about what will happen in future) occurs. The S-REF model specifies that such perseverative thinking is activated by metacognitive beliefs about the usefulness of worry and rumination: e.g. “worry will help me cope”. Unfortunately, worry and rumination achieve the opposite, because they increase negative thoughts and broaden the sense of threat. The individual repeatedly acts as if the negative thought is valid and important, preventing the development of a more flexible relationship with thoughts that can reduce worry and rumination. Similarly, the S-REF model explains how threat monitoring (e.g. scanning for symptoms or for negative thoughts) is driven by metacognitive beliefs that this strategy will be helpful, whereas it has the opposite effect by maintaining the sense of threat and personal vulnerability so that emotional distress persists or escalates.

Metacognitive therapy (MCT) modifies the beliefs and cognitive processes that maintain distress using a range of well-specified strategies and techniques outlined in a treatment manual [19]. Clinical application of MCT differs in important ways from Cognitive Behaviour Therapy (CBT) – the current gold standard treatment for anxiety and depression in cancer patients. CBT focuses on reality-testing negative thoughts or core beliefs, whereas MCT targets cognitive processes (worry/rumination) rather than challenging cognitive content. For example, common concerns in cancer patients are fear of recurrence or functional limitations associated with the disease and treatment. By contrast with CBT, MCT would not challenge the content of these potentially accurate thoughts or explore their ‘meaning’. Instead patients would be helped to understand the deleterious and counterproductive effects of worry and rumination, therefore enhancing motivation to suspend worry. Simultaneously, metacognitive beliefs about the uncontrollability of worry, which sustain worry, would be challenged using established MCT techniques, helping patients to suspend worry and rumination. Modifying negative metacognitive beliefs is centrally important in the S-REF model because, as long as patients believe that worry is uncontrollable, they will not attempt to control it. Therefore, in targeting cognitive processes rather than cognitive content, MCT offers a particularly close ‘fit’ with the needs of cancer survivors indicating potential for greater efficacy.

The evidence base for MCT is firmly established, with well over 150 empirical studies supporting the underpinning theory [19]. Metacognitive beliefs and processes have been implicated in emotional distress in diverse conditions including coronary heart disease, chronic obstructive pulmonary disease, chronic fatigue syndrome, Parkinson's disease, diabetes, and in cancer patients at all stages of the treatment trajectory [20-27]. Moreover, in terms of treatment outcomes, MCT is more effective than both wait-list control (Hedge's $g=1.18$) and CBT (Hedge's $g=0.97$) for anxiety and depression in mental health settings [28].

Translation of metacognitive theory and therapy to cancer is under way, with encouraging evidence for the explanatory and therapeutic utility of MCT in cancer. In patients with recently diagnosed breast cancer and prostate cancer, metacognitive beliefs predicted anxiety, after controlling for severity of worry and negative health beliefs [29]. In the first prospective study on the role of metacognition in breast and prostate cancer patients ($n=206$), metacognitive beliefs around the time of diagnosis predicted anxiety, depression and trauma symptoms 12 months later, after controlling for symptoms and cognitive beliefs at baseline [30]. We have conducted one open trial in young adult survivors of paediatric cancer (12 patients aged 18-24). MCT was highly acceptable and reduced anxiety, trauma symptoms and depression, with treatment gains maintained though to six months follow-up [31]. We are currently analysing data from a second open trial of MCT in a broader population of cancer survivors; preliminary data corroborate previous findings and indicate the effectiveness and acceptability of MCT to adult cancer survivors.

Given the growing evidence of its efficacy across a range of emotional disorders in mental health settings and potential efficacy in a range of cancer survivors, it is important now to further develop MCT for the broader cancer population, to evaluate its efficacy, and to determine the most effective form of delivery.

5. STUDY OBJECTIVES

The primary aim is to conduct an open trial of group MCT for cancer survivors experiencing clinically significant emotional distress.

Specific objectives are to:

1. Obtain evidence of potential efficacy of group MCT in alleviating emotional distress in cancer survivors.
2. Assess the acceptability of the intervention to patients.
3. Obtain data to inform sample size calculations for a subsequent Phase II trial
4. Determine whether group MCT for cancer survivors can be easily delivered in routine clinical practice

6. STUDY DESIGN

6.1. Design

An open trial (single arm, single site) with follow-up at 3 and 6 months.

6.2. Study Measures

All outcome measures will be administered pre-treatment, post treatment and at 3- and 6-months follow-up.

(i) Primary outcome:

Hospital Anxiety Depression Scale (HADS) [32] total was chosen because: 1) it has proven construct validity for measuring emotional distress in cancer patients [33], and 2) it is the optimal measure of general distress for evaluating treatment efficacy in heterogeneous cancer populations [34].

(ii) Secondary outcomes:

Cognitive Attentional Syndrome-1 [19] will assess rumination and worry. A single measure rather than separate measures of rumination and worry will reduce patient burden.

Fear of Cancer Recurrence Inventory [35] will assess fear of recurrence

Impact of Events Scale-Revised (IES-R) [36] will assess trauma related symptoms.

Metacognitions Questionnaire-30 (MCQ-30) [37] will assess metacognitive beliefs.

Functional Assessment of Cancer Therapy-General (FACT-G) [38], will assess cancer-specific quality of life.

(iii) Sample characteristics and potential covariates: We will record socio-demographic characteristics, time and nature of cancer diagnosis, psychiatric history, and previous and current treatment including any psychotropic medication.

6.4. Study Duration

Each participant will be involved in the study for 9 months and the total duration of the study will be 15 months.

7.1. Inclusion Criteria

- (i) Cancer diagnosis at least 6 months previously
- (ii) Scoring >15 on the full scale score of the Hospital Anxiety and Depression Scale (HADS) [32]
- (iii) Sufficient understanding of English to consent and engage in therapy
- (iv) Stable on, or free from, psychotropic medication
- (v) Minimum of 18 years old

7.2. Exclusion Criteria

- (i) History of psychotic disorder, learning disability, or organic mental disorder
- (ii) Risk of self-harm or suicide warranting immediate intervention
- (iii) In palliative phase of treatment
- (iv) Being considered for risk-reducing or reconstructive surgery within 1 year
- (v) Concurrent psychological intervention for emotional distress
- (vi) Cognitive impairment precluding informed consent or participation
- (vii) Undergoing acute medical treatment (e.g. chemotherapy, radiotherapy)
- (viii) Current drug/alcohol abuse

7.3 Ineligible and non-recruited participants

Patients who are ineligible or decline to participate at any point will continue to be offered usual care by CHPS.

7.4 Discontinuation of participants

Participants may withdraw from the trial at their own request at any time, without any consequences to themselves, their healthcare or their ability to take part in future research.

¹ All psychologists within the Clinical Health Psychology Service will be fully briefed about the study and its eligibility criteria by members of the research team prior to study commencement. To aid determination of eligibility during assessment appointments, each psychologist within the service will also be provided with a checklist of inclusion and exclusion criteria, against which they can screen patients during their assessment appointment. Please see enclosure.

8. ADVERSE EVENTS

8.1. Definitions

Adverse Event (AE): An AE is any untoward medical occurrence in a patient or clinical investigation subject administered a pharmaceutical product or study-specific intervention and which does not necessarily have a causal relationship with this intervention. Note: An AE may therefore be any unfavourable and unintended sign (including abnormal findings), symptom or disease concurrently associated with the use of the study intervention, regardless of any relation to the intervention.

8.2. Reporting Procedures

The Clinical Psychologists delivering group MCT will monitor patient's mental and physical health in accordance with good clinical practice guidelines. Any adverse events identified as likely to be caused by the intervention during the period of recruitment or intervention on the GMAC study will be recorded at the study site using a AEs/SAE record form which will be completed by the health professionals. The study CI, [name] will be informed and information inputted onto a secure database. The CI will also assess whether the nature of the event suggests that it is likely to have been induced as a result of the study intervention or processes.

One hypothesised adverse event which could occur due to the study intervention is as follows:

- Lowered mood and suicidality – a patient could become lower in mood or suicidal as a result of discussing their current health status.

Our proposed intervention does not withhold or significantly alter patient's usual medical care. The group MCT intervention is designed to improve patient's mood. However it is acknowledged that thinking or talking about distress can worsen mood or anxieties for some patients although this effect is rare and usually transient and is no more likely to occur with group MCT than with any other form of psychological treatment. However, in the event that patients feel more distressed following the intervention these patients will have access to continuing assessment and treatment by the CHPS.

The time period for detecting and recording AEs and SAEs in participants will be from the point of study inclusion until the end of the intervention.

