9.2 Power calculation

The primary indicator of efficacy will be change in HADS total between pre-treatment and 6-months follow up. In a recently completed open trial of MCT, the estimated between-patient standard deviation was approximately 7. As this is based on a small number of patients (n=20), a between-patient standard deviation of 12 will be used. No information on within-patient standard deviation is available so the between-patient standard deviation is used as a conservative measure. A trial with 95% power to detect a reduction in HADS score of 8 points, which is the minimum reliable difference we seek to obtain between baseline and 6 months follow up, requires 24 patients (one-sided alpha = 0.01). To account for clustering by group we will increase the sample size by a factor of 1.10 (1+ (average cluster size-1)) x intra-class correlation coefficient), therefore the required sample size will be 27.

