9.3 Analysis Plan

Descriptive analysis will explore the acceptability of group MCT by examining the number of eligible participants who took up the offer of intervention and the retention rate. Analysis will test treatment effects across time (baseline, post-treatment, and 6-month follow-up) using repeated measure analysis of variance. Main effects will be followed by Bonferroni corrected pairwise comparisons for each outcome. Within-group effect size (Hedges' g) will be calculated for ITT and completer samples and will be used to estimate the required sample size for a full randomised trial. Clinical significance of treatment effects will be assessed using the Jacobson method [39] to establish whether participants could be considered recovered as a result of treatment. This method allocates each patient to one of four possible outcomes: (1) reliable deterioration; (2) no change; (3) reliable improvement; and (4) recovered. The first three outcomes are derived solely from a reliable change index (RCI) which compares treatment outcomes to normative data from non-clinical samples to determine whether the magnitude of change is statistically significant. To be classified as 'recovered', patients need to demonstrate both a reliable change and a score that falls below the established clinical cut-off. Therefore patients will be classified as 'recovered' where post-treatment HADS total <13, RCI will be 8 based on normative data from a large non-clinical sample [40].

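### Section 8.2 closes AE and SAE recording at the end of the six-session therapy, while efficacy is judged at 6 months

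*Protocol*

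**What the plan says.** Section 8.2 of the protocol ends the safety window with the intervention, in its last sentence (final word omitted here): "The time period for detecting and recording AEs and SAEs in participants will be from the point of study inclusion until the end of the". An earlier sentence in the same section describes what is recorded: "Any adverse events identified as likely to be caused by the intervention during the period of recruitment or intervention on the GMAC study". These events go on an AE/SAE form, the CI is informed, and the CI assesses whether the intervention or study processes are the likely cause.

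Section 8.2 gives one hypothesised harm: "a patient could become lower in mood or suicidal as a result of discussing their current health status". It then provides that "in the event that patients feel more distressed following the intervention these patients will have access to continuing assessment and treatment by the CHPS".

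The efficacy timetable is longer. Section 6.3 describes six weekly sessions. Sections 6.1 and 6.2 schedule questionnaires, HADS included, before treatment, after treatment and at 3 and 6 months. Section 9.2 says: "The primary indicator of efficacy will be change in HADS total between pre-treatment and 6-months follow up". Section 6.4 puts each participant's involvement at 9 months.

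**The concern.** The protocol follows each patient for months after therapy to see whether benefit lasts, but its formal record of harm stops when therapy stops. The harm it expects, worsening mood and suicidality, can plausibly arise or continue after the last session, and section 8.2 allows for distress at that stage. What it offers then is clinical care, which is not the same as recording.

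This matters because the open trial is meant to support a move to a randomised phase II trial. Its report would set efficacy at 6 months beside a harms record covering only the time from inclusion to the last session. A suicidal crisis at month 4, for example, would call for no SAE form and no causality review under the plan as written, and readers of the harms table could not tell that this period had not been covered.

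**Working it through.** The check compares passages of the protocol, with a small calculation of the time left uncovered. The protocol states no figure of its own to reproduce.

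**Is recording extended anywhere else?** No. Section 8.2 is the only place that sets a window. Section 6.2 adds questionnaires at 3 and 6 months but no AE enquiry. Section 7.4 covers withdrawal and does not mention AEs. Because the protocol fixes the window itself, this is not a detail left to an analysis plan.

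**Inputs**
- Therapy: six weekly sessions (6.3). Session 1 to session 6 spans 5 weekly intervals, so 5 weeks; counted as six treatment weeks, 6.
- Follow-up: 6 months (6.1), taken as 52/2 = 26 weeks.
- Involvement: 9 months (6.4), or 9 × 52/12 = 39 weeks.
- Origin of the 6 months: not stated, so both options are shown.

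**Share of time from session 1 to the primary time point outside the AE window**

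| Follow-up timed from | Therapy 5 weeks | Therapy 6 weeks |
|---|---|---|
| End of therapy | 26/(5 + 26) = 26/31 = 84% | 26/(6 + 26) = 26/32 = 81% |
| Session 1 | (26 − 5)/26 = 21/26 = 81% | (26 − 6)/26 = 20/26 = 77% |

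The share is about four fifths on either reading.

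Against the full 9 months, with all time outside follow-up counted as covered, the share is 26/39 = 67% if follow-up starts at the end of therapy, and 21/39 = 54% or 20/39 = 51% if it starts at session 1.

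**Does HADS fill the gap?** Only in part.
- It shows worsening mood at 3 and 6 months in patients who complete it. No HADS result is linked to an AE form, CI notification or causality review.
- It says nothing about events between assessments.
- Section 9.1 allows for 40 recruited and 27 remaining at 6 months, so 40 − 27 = 13 participants may have no 6-month score.
- No measure listed in 6.2 is described as assessing suicidality.

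**Which events qualify?** Section 8.1 defines an AE whether or not it is related to the intervention. Section 8.2 records only AEs thought likely to stem from the intervention, and then asks the CI to judge that same question. The filter precedes the assessment, so lengthening the window alone would still leave out events nobody at the site had attributed to therapy.

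**The case against.** The strongest defence is that the window is deliberate and fits the stated mechanism. Section 8.2 ties the risk to talking about health during therapy and describes any worsening as uncommon and short-lived. Distressed patients keep access to the psychology service, where the therapists work (6.3). Those therapists sit on the management team (11), and section 10.4 allows disclosed risk of harm to be passed to other clinicians. Late events are therefore not clinically abandoned. That stands, but none of it creates a study record.

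Several stronger readings are tempting, and the protocol does not support them:
- *Worsening mood after therapy goes unmeasured.* It does not, since HADS is repeated at 3 and 6 months. What is missing is formal AE/SAE recording.
- *A late event could never reach the CI.* It could do so informally through service staff. The accurate statement is that no procedure requires it.
- *Section 8.2 contains two contradictory windows.* The phrase "during the period of recruitment or intervention on the GMAC study" reads naturally as each patient's time from entry through therapy, which agrees with the closing sentence. A conflict appears only if it is read at study level. The wording should be tidied, but it is not a contradiction.
- *The report will show patients classed as reliably deteriorated at follow-up beside zero AEs.* Section 9.3 says "This method allocates each patient to one of four possible outcomes: (1) reliable deterioration; (2) no change; (3) reliable improvement; and (4) recovered", but it defines recovery on post-treatment HADS and does not say that the classes are applied at 3 or 6 months. Such an output is possible but not planned.
- *A planned benefit-harm estimate is biased.* The protocol states no safety objective and no such estimate. The problem is unequal reporting periods.

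On cost, the protocol does not say whether follow-up questionnaires are completed in person, by post or by telephone, and section 10.7 says the study is unfunded. An added question could therefore take somewhat more effort than it appears.

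**Conclusion.** The point holds in this limited form: formal AE and SAE recording ends with therapy, although follow-up and the efficacy judgement run to 6 months and the protocol's own named harm may appear in between. About 77% to 84% of the time from session 1 to the primary time point is uncovered. That range assumes a 26-week half-year and five or six weeks of therapy, and it spans both possible origins of follow-up. The 67% figure for the full 9 months should not be read as a minimum, because it requires follow-up to be timed from the end of therapy.

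The efficacy estimate is unaffected. The consequence is an incomplete harms record for suicidality, for events between assessments and for events in patients who drop out. It is worth correcting because the correction is cheap.

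**What to change.** Amend section 8.2 as follows:

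1. State one per-participant window, from consent to the 6-month follow-up assessment, and bring the earlier phrase about the recruitment or intervention period into line with it.
2. Ask about AEs and SAEs at the existing post-treatment, 3-month and 6-month contacts, with the form and CI notification already described in 8.2.
3. Reconcile the rule on which AEs are recorded with the definition in 8.1, so that causality is assessed after recording and is not a condition for it.
4. Report any reliable HADS deterioration alongside the AE record. Making every 8-point rise an automatic AE is unnecessary, and it would clash with the causality filter as it now stands.

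The cost is a short protocol amendment and one added question at contacts already scheduled, with some extra effort if those contacts are postal. The downside is a few more AE forms, many for unrelated or cancer-related events, and a less favourable harms count.
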